Specific Aim 3: Investigate the extent to which tDCS modifies resting state network segregation.

Hypothesis 3: Compared to the sham tDCS group, the active tDCS group will demonstrate improved segregation of resting state networks at post-training relative to baseline.

[figure not shown]
6. Research Plan:

Study Overview

Screening	Baseline	Locomotor Learning	Post (1 Day)	Post (1 Week)	Post (1 Month)
1 Visit	1-2 Visits	4 Visits	1 Visit	1-2 Visits	1 Visit

 • Informed Consent • Cognitive Function • Walking Function 	
 • Obstacle walking with fNIRS • Cognitive Function • MRI: 
 › Structural › Resting state › Task-based (imagined obstacle walking) • Blood Draw 	
 • Active or sham tDCS during: • Obstacle task practice 
 1 - blocked practice 2 - variable practice 3 - combined practice 4 - full task practice 	
 • Obstacle walking with fNIRS 	
 • Obstacle walking with fNIRS • Cognitive Function • MRI: 
 › Structural › Resting state › Task-based (imagined obstacle walking) • Blood Draw 	
 • Obstacle walking with fNIRS • Cognitive Function

Up to one hundred older men and women will be enrolled in the intervention component of this study. An additional 15 participants (estimated) may enroll in the intervention but discontinue participation before completing the protocol. A larger number (up to 400) may participate in screening by telephone and/or onsite, but will fail the screening tests and not proceed to the study intervention. Participants will undergo the following sequence of events:

- *Telephone Screening*: Participants will be screened by telephone to determine if they meet basic enrollment criteria including age and general health status. If patients authorized us to view their medical records, those records may be examined to verify absence of exclusion diagnoses, to obtain complete/accurate medication lists, and to assess whether participants have successfully completed prior MRI scans.

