For Specific Aim 1 we seek to determine whether active tDCS is superior to sham tDCS for enhancing retention of locomotor learning after one week. The primary outcome is the change in walking speed on the obstacle course between the end of the learning period to the one week post visit. We are powering the study to detect group differences in retention of walking performance. We will use an ANOVA model to test group differences, and will account for demographic covariates. To estimate sample size for this aim, we have conducted a pilot study with 12 older adult participants who were randomized to an active (n=5) or sham (n=7) tDCS group. To assess retention, the mean walking speed from the final three trials of the learning session were compared to the mean walking speed from the three retention trials measured one week later. The active tDCS group showed a between-session gain in walking speed of nearly 0.07 m/s. The sham tDCS group showed a drop in between-session speed of approximately -0.04 m/s. This between group-difference of 0.1 m/s is considered clinically meaningful and had a large effect size of 0.87. The whole-group standard deviation of response was 0.12. Based on these preliminary data, we will need 48 participants (n=24 per group) to detect a statistically significant group difference at alpha=0.05 and beta=0.20 (i.e., 80% power). To be conservative, we will enroll 60 participants to account for potential dropout and to ensure sufficient statistical power.

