For Specific Aim 2 we seek to determine if several key measures of brain integrity/function help to explain individual differences in the retention of locomotor learning after one week. We will use multivariate regression models that account for demographic covariates. Based on the assumptions of univariate linear regression, a sample size of 60 with alpha=0.05 and beta=0.20 (i.e., 80% power) will allow us to significantly detect correlations coefficients as small as 0.355. Values below this level are generally considered very weak, and thus there would be little benefit to powering the study to detect smaller values. Based on our pilot data and findings from the literature, we are very likely to observe stronger associations that will achieve statistical significance. For instance, our pilot data show that working memory performance and prefrontal activation are associated with visuomotor learning with correlations of 0.57 and 0.48, respectively. Our pilot data also show that resting state default mode network connectivity is associated with retention of learning with a correlation of 0.46. Our statistical models will account for a number of demographic and other covariates, thereby accounting for some of the variability in the data set and improving our ability to detect these mechanism-related associations.

For Specific Aim 3 we seek to acquire evidence that tDCS modifies resting state network connectivity and segregation during motor learning. Prior studies have shown that even a single session of motor learning or a single session of tDCS can modify the connectivity of resting state brain networks. However, this remains an exploratory aim and we have not specifically powered the study for this purpose. Nevertheless, as with the other measures described above, if the effect size is moderate or large we are likely to detect it with statistical significance.

Data and Safety Monitoring Plan

Adverse Event Reporting

Adverse events will be reported according to the guidelines of the University of Florida Institutional Review.

Reporting within 5 days of the PI becoming aware will apply to adverse events that meet all of the following criteria:

- Serious
- Unexpected
- Related or the Relationship is “more likely than not”

Adverse events will be added to the cumulative event table and reported at continuing review when they meet either of the following criteria:

- Serious (but expected) and related or the relationship is “more likely than not”.

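### The sample size is stated three ways (a limit of 100 plus about 15 discontinuers, 60 enrolled including dropout, 60 analysed for Aim 2), so the Aim 1 and Aim 2 figures do not rest on one number

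*Combined protocol and SAP*

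**What the plan says.** Section 6 (Research Plan, Study Overview) gives an upper limit: "Up to one hundred older men and women will be enrolled in the intervention component of this study". The next sentence adds people outside that count: "An additional 15 participants (estimated) may enroll in the intervention but discontinue participation before completing the protocol". Taken together, about 115 people could enter the intervention.

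Section 10 (Statistical analysis and sample size calculations), under Aim 1, derives a requirement: "we will need 48 participants (n=24 per group) to detect a statistically significant group difference at alpha=0.05 and beta=0.20". It then sets the enrolment: "To be conservative, we will enroll 60 participants to account for potential dropout and to ensure sufficient statistical power". Here the dropout allowance lies inside the 60.

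Under Aim 2, Section 10 uses the same number as if all 60 were analysed: "a sample size of 60 with alpha=0.05 and beta=0.20 (i.e., 80% power) will allow us to significantly detect correlations coefficients as small as 0.355".

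Section 6 (Informed Consent and Onsite Screening Visit) also lets people take part without MRI. Neither 60 nor 100 is divided by MRI status.

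**The concern.** A sample-size statement should let a reader identify the number randomised, the number expected in the analysis, and the power or detectable effect at that second number. Here the number 60 serves as both enrolled and analysed within one section, and another section gives a different upper number with a different way of counting discontinuers. No sentence says which number ends enrolment.

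Two things are at stake. First, at least one stated operating figure must be wrong for the trial as described, because 60 cannot both absorb dropout and be fully analysed. Second, with an undefined end to enrolment, a final size of 60 or of 100 would each agree with some part of the protocol. A later reader could not confirm that the size was fixed in advance and independently of the results.

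**Working it through.** **Inputs.** From Section 10: difference 0.10 m/s ("This between group-difference of 0.1 m/s is considered clinically meaningful and had a large effect size of 0.87"), SD 0.12 ("The whole-group standard deviation of response was 0.12"), alpha 0.05, power 80%, 48 needed, 60 enrolled, Aim 2 detectable r 0.355 at 60. From Section 6: up to 100, plus an estimated 15. The protocol does not state sidedness. I assume two-sided, because one-sided calculations give 34 to 38 in total and do not reproduce 48.

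**1. Reproducing Aim 1.** d = 0.10/0.12 = 0.833. The normal approximation gives n per group = 2(1.960 + 0.842)²/0.833² = 22.6, so 23. The t-test version gives 23.6, so 24 per group and 48 in total, as stated. (The quoted effect size of 0.87 would give 42 to 44, so 48 rests on 0.10 and 0.12. This side point does not affect what follows.)

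**2. From 48 to 60.** 60 − 48 = 12, and 12/60 = 20%; equivalently 48/(1 − 0.20) = 60. Section 6 implies 15/115 = 13%. Both rates are inferred; the protocol states none.

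**3. Reproducing Aim 2.** Detectable r = tanh[(1.960 + 0.842)/√(N − 3)]. For N = 60: 2.802/√57 = 0.371, and tanh(0.371) = 0.355, as stated. This holds only if all 60 are analysed.

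**4. Both aims at each size.** Aim 1 power uses the noncentral t with noncentrality 0.833 × √(n per group/2), which is 2.89, 3.23 and 4.17 for 24, 30 and 50 per group.

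| Number analysed | Aim 1 power | Aim 2 detectable r |
|---|---|---|
| 48 | 80.7% | 0.395 |
| 60 | 88.8% | 0.355 |
| 100 | 98.5% | 0.277 |

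The 80% power quoted for Aim 1 belongs to the first row and the 0.355 quoted for Aim 2 to the second. Keeping 60 analysed after 20% loss would need 60/0.80 = 75 enrolled.

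**5. MRI measures.** Gray matter volume and network segregation come only from participants who have MRI, and their number is not given. As assumptions: with 40 analysed, r = tanh(2.802/√37) = 0.43; with 30, r = tanh(2.802/√27) = 0.49. The pilot correlation quoted for default mode connectivity, 0.46, is detectable with 80% power once N reaches 3 + (2.802/0.497)² = 34.7, so 35.

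**6. Hypothetical only.** If the one-week comparison were tested at 0.05 with 60 analysed and, if not significant, again with 100, the two test statistics would have correlation √(60/100) = 0.775 and the overall two-sided error would be about 0.08. The protocol plans no such look.

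**The case against.** The strongest reply is that there is no strict contradiction. The Section 6 number is a maximum, set beside other planning estimates such as the screening limit of 400, while Section 10 gives a definite commitment to 60, which lies within that maximum. This is a reasonable reading and may be what is meant. It does not explain why discontinuers are added on top in one place and absorbed in the other, and it leaves the double use of 60 inside Section 10 untouched.

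It can also be said that a larger sample does no harm. That stands for power: any analysed number from 48 to 100 meets the 80% target for Aim 1, and at 100 both stated figures would be conservative.

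A reader might go further and infer several things that the protocol does not support:

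- **That discontinuers are replaced, or that a completer-only sample is built.** No replacement rule is stated. An enrolment count does not define an analysis set, and nothing excludes discontinuers from analysis.
- **That the dropout rate is concealed.** Section 6 counts discontinuers separately, which if anything makes them visible.
- **That 13% and 20% are conflicting dropout assumptions.** Both are back-calculated, and Section 10 gives two reasons for the extra 12, of which dropout is only one.
- **That type I error is inflated.** The 0.08 depends on an interim look that is not planned. Silence on interim looks is not evidence of one.

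**Conclusion.** The point holds as an inconsistency in the stated sample size and in the figures built on it. It does not show an underpowered primary comparison or a loss of alpha control.

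The definite error is in Aim 2: if 60 are enrolled and the full allowance of 12 is lost, the detectable correlation is about 0.395 rather than 0.355, and it is larger for MRI-based measures by an amount that depends on an unstated MRI count. The practical effect is modest, since the pilot correlations quoted in Section 10 (0.46, 0.48 and 0.57) all exceed 0.395. The remaining problem is that the end of enrolment is not defined.

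These results assume two-sided tests, equal groups, the protocol's own difference and SD, and, for the 48, that all 12 extra participants are lost. With fewer losses the detectable r lies between 0.355 and 0.395.

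**What to change.** Make one wording amendment across Sections 6 and 10:

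- State a single randomisation target in both sections. Either label 100 explicitly as an administrative ceiling or make it the target.
- Say whether people who discontinue count toward the target, and give the assumed dropout rate.
- Restate Aim 1 power and the Aim 2 detectable r for the number expected to be analysed. For 60 enrolled and 48 analysed, these are about 81% and about 0.395. Give a separate figure for MRI measures, based on the expected number with MRI.
- Add that enrolment ends at the target without reference to results by arm.

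Fixing 60 randomised without restating Aim 2 would not be enough, because it would leave 0.355 in place with about 48 analysed. The cost is a slightly less favourable Aim 2 figure and less freedom to keep enrolling; no study procedure changes.

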- *Informed Consent and Onsite Screening Visit*: Participants who pass the phone screen will be invited to participate in on-site screening. Informed consent will be obtained. Mobility function, cognitive function, and health/safety screening will be conducted. This single visit will last approximately 3.5 hours. Qualifying participants will be invited to participate in the full study with or without MRI.
- *Baseline* Participants will undergo a test of walking over obstacles, turning while walking (90 degree turns and 180 degree turns), turning while standing in place (360 degree turn), cognitive function, blood draw, and MRI scans at the UF McKnight Brain Institute (structural, functional, and resting state MRI scans) if MRI screening passed. Baseline assessment will last about 4 hours and may be completed over 1 or 2 visits based on scheduling flexibility of the participant, study personnel, and equipment.
- *Study Intervention Visits*: Participants will attend four intervention sessions in which they will practice a “locomotor learning” task comprised of a 10m walking course with obstacles and transitions between hard and soft floor surfaces. During this task they will receive either active or sham transcranial

The obstacles walking task includes a series of foam obstacles and foam mats. This walking task is used for baseline visits, study intervention visits, and post visits.

direct current stimulation (tDCS) to the frontal portion of the brain. Each visit will last approximately one hour.

- **1-Day Post Assessment:** Participants will undergo a test of walking over obstacles.
- **1-Week Post Assessment:** Participants will undergo a test of walking over obstacles, cognitive function assessment, blood draw, and MRI scans (MRI eligible participants only) at the UF McKnight Brain Institute (structural, functional, and resting state MRI scans). Post assessments will last about 4 hours and may be completed over 1 or 2 visits based on scheduling flexibility of the participant, study personnel, and equipment.
- **Visit 9: 1-Month Post Assessment:** Participants will undergo a test of walking over obstacles, turning tasks, and cognitive function assessment. This visit will last approximately 2 hours.

Telephone Screening

Participants will be screened by telephone to determine if they meet the following criteria:

Inclusion criteria

- Age 65 - 95 years

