- Willingness to be randomized to either intervention and to participate in all aspects of study assessment and intervention

Exclusion criteria

- Diagnosed neurological disorder or injury of the central nervous system, or observation of symptoms consistent with such a condition (spinal cord injury, Alzheimer's, Parkinson's, stroke, etc.)
- Contraindications to non-invasive brain stimulation (e.g., metal in head, wound on scalp)
- Contraindications to MRI (claustrophobia, metal anywhere in body, etc.).
- Use of medications affecting the central nervous system including, but not limited to, benzodiazepines, anti-cholinergic medication and GABAergic medication.
- severe arthritis, such as awaiting joint replacement
- current cardiovascular, lung or renal disease; diabetes; terminal illness
- myocardial infarction or major heart surgery in the previous year
- cancer treatment in the past year, except for nonmelanoma skin cancers and cancers having an excellent prognosis (e.g., early stage breast or prostate cancer)
- current diagnosis of schizophrenia, other psychotic disorders, or bipolar disorder
- difficulty communicating with study personnel (including people who cannot speak English)
- uncontrolled hypertension at rest (systolic > 180 mmHg and/or diastolic > 100 mmHg)
- bone fracture or joint replacement in the previous six months
- current participation in physical therapy for lower extremity function or cardiopulmonary rehabilitation
- current enrollment in any clinical trial
- clinical judgment of investigative team

Informed Consent and Onsite Screening Visit

Upon arriving to the research site, participants will undergo informed consent. We will explain the full study protocol including transcranial direct current stimulation and MRI.

All questions from the phone screening will be repeated, and additional health/medical screening criteria will be evaluated. This will include:

- Resting blood pressure
- Basic visual examination with Snellen eye chart
- Height, weight, age, sex, education level, socioeconomic status
- Medical history
- Obtain list of medications that the participant is currently using
- Various walking tasks including typical walking, fast walking, walking over obstacles, walking while carrying a tray, and combinations of these tasks.
- Somatosensory assessments of the foot based on tactile pressure sensation.

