- Activities Specific Balance Confidence Scale: 16-item questionnaire that gauges confidence (on a scale of 0-100%) on various balance and walking tasks relevant to household and community ambulation.
- Berg Balance Scale: 14-item assessment of balance task performance to assess balance ability and fall risk.
- Movement-specific Reinvestment Scale: questionnaire that asked about the extent to which a person directs conscious attention to control of movement.
- Montreal Cognitive Assessment (MoCA)
- Trailmaking Test – paper based test where the person must “connect the dots” between numbers or between alternating letters and numbers.
- Sleep quality assessed by the Pittsburgh Sleep Quality Index, which is a questionnaire about sleep-related habits and experiences.

Following the screening visit, study staff will evaluate performance/responses relative to the study enrollment inclusion/exclusion criteria. BMI will be calculated from the height and weight collected. Medical records may be examined to verify absence of exclusion diagnoses, to obtain complete/accurate medication lists, and to assess whether participants have successfully completed prior MRI scans. Individuals who meet all criteria will be invited to enroll in the full study. Participants who screen out of MRI may also be invited to enroll for the study with the MRI portion excluded.

At the discretion of the Principal Investigator, any individual may be deemed ineligible for further participation in this study if there are concerns about the individual's capability to perform study procedures or if it may be unsafe for the volunteer to participate in the study. Furthermore, minor exceptions to the inclusion/exclusion criteria may be permitted at the discretion of the Principal Investigator if those exceptions do not influence participant safety. For example, if a participant walks somewhat faster than the target inclusion criteria for walking speed. This is important to ensure that individuals are not excluded for insignificant reasons and to facilitate meeting enrollment benchmarks.

Baseline Visit(s)

[figure not shown]

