Magnetic resonance imaging is considered a safe, and there are no known long term effects from short term exposure to magnetic fields. The primary risk is to people with implanted metallic objects or medical devices, which could move or heat up as a result of the magnetic field. This could cause injury or discomfort. We will screen our participants carefully to ensure that no metal objects are present in or on their bodies. Another risk is that metal objects within the MRI testing area could become projectiles. We will be careful to ensure that no metal objects are present in the testing area. Some participants report claustrophobia while inside the scanner. Participants are screened for known claustrophobia before participating (and this is a contraindication for participation). If a participant begins to experience symptoms of claustrophobia during the scan, they will have the option of discontinuing the scan at any time. The scanner produces a loud noise, so participants will be provided with earplugs and/or MR-compatible headphones to alleviate any potential discomfort or possible hearing damage due to this loud noise.

fNIRS is considered safe. The infrared light used in assessment is not known to cause any harm or to alter the brain in any way. The sensors are secured to the participant's head using adhesive tape, which may cause minor skin irritation in some people, particularly those who are sensitive/allergic to adhesives. We will check with participants about any known sensitivities to adhesives.

Skin conductance involves placing adhesive electrodes on two fingers of each hand. It is sometimes slightly uncomfortable to remove the electrodes because they are very sticky.

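### MRI contraindication excludes at telephone screening, yet enrolment without MRI is allowed; the Aim 2 detectable correlation of 0.355 then does not carry over to the MRI measures

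*Combined protocol and SAP*

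**What the plan says.** **Text that excludes.** In section 6, under Telephone Screening, the exclusion criteria list "Contraindications to MRI (claustrophobia, metal anywhere in body, etc" as a plain item. The inclusion criteria ask for "Willingness to be randomized to either intervention and to participate in all aspects of study assessment and intervention". Under Possible Discomforts and Risks, the MRI paragraph says "Participants are screened for known claustrophobia before participating (and this is a contraindication for participation".

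**Text that permits.** The onsite screening bullet in the section 6 Study Overview says "Qualifying participants will be invited to participate in the full study with or without MRI". The later subsection on informed consent and onsite screening says "Participants who screen out of MRI may also be invited to enroll for the study with the MRI portion excluded". Four further statements make scanning conditional on MRI eligibility: the baseline and 1-week bullets of the Study Overview, the Magnetic Resonance Imaging subsection, and Post Visits.

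**Order of screening.** The Study Overview invites onsite only people who have passed the telephone screen. The telephone questions are then repeated at the onsite visit.

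**Numbers.** Section 10 states for Aim 2 that "a sample size of 60 with alpha=0.05 and beta=0.20 (i.e., 80% power) will allow us to significantly detect correlations coefficients as small as 0.355". For Aim 1 it requires 48 participants and enrols 60 to allow for dropout. The Study Overview allows up to 100 in the intervention component. No section says how many participants are expected to be scanned.

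**The concern.** There are two linked problems.

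The first is operational. A person with a known contraindication fails the telephone list and never reaches the onsite paragraph that would admit them. Two members of staff, each following the protocol, could decide differently about the same caller. The make-up of the sample would then depend on local practice rather than on a stated rule.

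The second is statistical. Aim 2 mixes measures that everyone can provide (working memory, fNIRS) with measures that exist only for scanned participants (gray matter volume, network connectivity). Section 10 quotes a single detectable correlation for all of them, based on 60. If some of the 60 enrolled are not scanned, the MRI hypotheses have less sensitivity than the plan states, and a null result on them could be read as stronger evidence than it is.

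**Working it through.** **1. The conflict, side by side.** Take a caller who reports claustrophobia.
- Telephone exclusion list: excluded, and so not invited onsite.
- Onsite screening text: may be enrolled with the MRI portion left out.

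The exclusion item does not refer to the onsite permission. The investigator's discretion clause covers only minor exceptions and does not mention MRI. The firm conflict is therefore one exclusion item against two explicit permissions.

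**2. Inputs for Aim 2 (section 10).** n = 60, alpha 0.05, power 80%, detectable r = 0.355, pilot default mode correlation 0.46. Sidedness is not stated.

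**3. Reproducing the plan's figure.** By Fisher z, two-sided:

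r = tanh[(1.960 + 0.842) / √(n − 3)]

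At n = 60: 2.802 / √57 = 2.802 / 7.550 = 0.371, and tanh(0.371) = 0.355. This matches. A one-sided test would give 0.318, so the plan evidently used two-sided alpha.

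**4. The same formula at smaller scanned numbers.** The scanned shares of 60 are assumptions. Power at a given r is Φ[atanh(r)·√(n − 3) − 1.960].

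| Share scanned (assumed) | n | Detectable r, 80% power | Power at r = 0.355 | Power at r = 0.46 |
|---|---|---|---|---|
| 100% | 60 | 0.355 | 80% | 96% |
| 90% | 54 | 0.373 | 76% | 94% |
| 80% | 48 | 0.395 | 70% | 92% |
| 70% | 42 | 0.421 | 64% | 87% |
| 60% | 36 | 0.452 | 57% | 82% |

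Example at n = 48: 2.802 / √45 = 0.418 and tanh(0.418) = 0.395. Power at 0.355 is Φ(0.371 × 6.708 − 1.960) = Φ(0.53) = 70%.

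**5. Scans needed for the pilot correlation.** n = (2.802 / atanh(0.46))² + 3 = (2.802 / 0.497)² + 3 ≈ 34.7, so 35.

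**6. The larger enrolment.** If 100 are enrolled and 60% are scanned, n = 100 × 0.60 = 60 and the detectable r is 0.355 again.

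**7. What each aim depends on.** Aim 1 is walking speed and uses no MRI, so its 48 is untouched. In Aim 2, gray matter volume and network connectivity need scans; working memory and fNIRS do not. Aim 3 rests wholly on MRI, but section 10 calls it exploratory and not powered.

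**The case against.** The best defence is that the intent is clear. The onsite text says what happens to people who screen out of MRI, and the remaining visit descriptions consistently treat scanning as conditional. On that view only a cross-reference is missing from the telephone list. The intent may well be so, but the telephone list is the gate. As written, it stops a known-contraindicated caller before the permission can apply.

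Two supporting passages are weaker than they look, and this part of the defence stands. The statement "and this is a contraindication for participation" covers claustrophobia only and sits in the MRI risk paragraph, so it may mean taking part in the scan. The criterion on all aspects of assessment concerns willingness, and a willing person can still be contraindicated. The conflict does not depend on either.

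A reader might also draw stronger conclusions that the documents do not support:
- **That the MRI analyses cannot reach 60.** The Study Overview allows up to 100. The scanned number is unsettled, not necessarily below 60.
- **That the MRI hypotheses are badly underpowered.** Even with 36 scanned, the pilot default mode correlation of 0.46 has about 82% power. What fails is the unqualified 0.355.
- **That 0.355 is wrongly claimed for Aim 3.** The plan never applies it there.
- **That the strict rule turns people away for no reason.** Aims 2 and 3 use MRI measures, which is an evident reason.
- **That randomisation must be stratified by MRI eligibility.** The documents do not say whether eligibility is settled before randomisation. The MRI safety form is completed and approved when the participant attends for the scan, and a scan can be stopped for claustrophobia.

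**Conclusion.** The point holds in two parts. The eligibility text contradicts itself on people with an MRI contraindication, and this needs no assumption. If non-MRI enrolment is allowed and 60 are enrolled, the stated 0.355 does not hold for gray matter volume or network connectivity, because it would require an analysable scan from every one of the 60, a number that already contains the dropout allowance.

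The size of the second part depends on a scan rate that the documents do not give. Over assumed losses of 10% to 40% of the 60, the detectable correlation rises by 0.018 to 0.097 (0.373 − 0.355 and 0.452 − 0.355). It does not rise if enrolment is large enough to yield 60 scans. The primary aim, and the non-MRI measures of Aim 2 when all 60 are analysed, are unaffected. This should be corrected, but it does not threaten the main comparison.

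**What to change.** 1. Reconcile the telephone exclusion item with the two onsite statements that permit enrolment without MRI, and align the claustrophobia remark in the risk section and the all-aspects inclusion criterion with the result. Which rule to keep is for the investigators; either can be made consistent.
2. If non-MRI enrolment is kept, define the MRI analysis set. H2a (gray matter) and H2c need a usable baseline scan; the gray matter change in H2b needs usable scans at both baseline and 1 week.
3. State the expected n of that set, and whether it is derived from 60 or from up to 100 enrolled.
4. Restate the Aim 2 detectable correlation for the MRI measures at that n, and keep 0.355 only for measures taken on all 60.
5. Optionally, stratify randomisation by MRI eligibility, but only if eligibility is settled beforehand.

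The cost is protocol wording and one restated figure, which will be somewhat less favourable if fewer than 60 are scanned. The required n for Aim 1 does not change.
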